11.2 Data Quality Assurance

This is an investigator-initiated trial. The private practice consists of an orthopedic surgeon and a part time medical assistant. The investigator is also the sponsor of the trial and is also responsible for quality assurance. A clinical monitor will verify the quality of the data.

11.3 Source Data

Definition of Source Data:

Source data includes all information in original records and certified copies of original records of clinical findings, observations, or other activities in a clinical investigation used for reconstructing and evaluating the investigation.

The source data in this clinical trial are the electronic patient charts. They are attributable, legible, contemporaneous, original, and accurate and meet regulatory requirements. For this trial, this includes the MRI, the PROM's, and the operative report (for the operated group). Data of patients who take part in the study will be transferred to the CRF in pseudonymized form. No date of birth or initials will be transferred. The pseudonymization list and the CRF will be only available to the orthopedic surgeon and the access is controlled and the hardcopy of the pseudonymization list and the CRF is saved in a safe. The investigator

permits trial-related monitoring, audits, IRB/IEC review and regulatory inspections providing direct access to source data/documents. The clinical monitor will regularly verify CRF-Data relative to source data. Safety of participants is protected and the conduct is in accordance with GCP.

12 APPENDIX: ADVERSE EVENTS AND SERIOUS ADVERSE EVENTS – DEFINITIONS, SEVERITY, AND CAUSALITY

12.1 Further Details and Clarifications on the AE Definition

There are no regional AE requirements. An adverse event log is filled to follow the adverse event until it is solved.

A trial related adverse event is redness, haematoma, swelling, infection of the operated site and pain of the treated knee. This will be recorded in the electronic patient chart and in the CRF.

Progression of osteoarthritis up to TKA does not meet AE definition; it is the normal progression of the disease and will be expected to be more observed in the non-operated group.

The IMP of this clinical trial is human cancellous bone, there is no dose, there are only dimensions of the transplant. Thus, there is no overdose.

Lack of efficacy of the procedure is provided when more than 20% of the procedures fail.

12.2 Further Details and Clarifications on the SAE Definition

SAEs must be reported immediately to the IRB/IEC except for those SAEs that the protocol identifies as not needing immediate reporting. Additionally SAEs related to the IMP are reported to the EudraVigilance Data base and via the CTIS webpage.

A trial related SAE is an allergic reaction against the IMP.

Progression of osteoarthritis up to TKA does not meet SAE definition; it is the normal progression of the disease and will be expected to be more observed in the non-operated group.

On the Webpage of the PEI there is a document

(<https://www.pei.de/DE/Arzneimittelsicherheit/gewebevigilanz/meldeformulare/meldeformulare-node.html>, Form G1a) to be filled in for :“ Meldung des Verdachts einer schwerwiegenden unerwünschten Empfängerreaktion im Zusammenhang mit der Übertragung von Gewebe, Gewebezubereitungen oder Stammzellen gemäß § 63i AMG“ this form would be filled and send to the PEI.

12.3 Severity

Definition Severity:

Severity is the intensity of a specific event. The event itself can be of minor medical significance.

- Grade 1: Mild — transient or mild discomfort (< 48 hours); no medical intervention/ therapy required.
- Grade 2: Moderate — mild to moderate limitation in activity — some assistance may be needed; no or minimal medical intervention/ therapy required.
- Grade 3: Severe — marked limitation in activity, some assistance usually required; medical intervention/ therapy required, hospitalization possible.
- Grade 4: Life-Threatening — extreme limitation in activity; significant assistance required; significant medical intervention/therapy required, hospitalization, or hospice care probable.
- Grade 5: Death.

12.4 Causality

Definition Causality: Causality is an influence by which one event, process, state, or object (a cause) contributes to the production of another event, process, state, or object (an effect) where the cause is partly responsible for the effect, and the effect is partly dependent on the cause. It is an evaluation of the likelihood that a particular treatment is the cause of an observed adverse event (AE).

Causality Categories:

- definitely related
- probable
- possible
- unlikely
- unclassified/unassessable
- Causality ruled out/unrelated

Procedure for assessing methodology: (WHO Methodology)

- definitely related: good timing, no other cause, withdrawal response plausible, rechallenge, "definite"
- probable: good timing, other cause unlikely, withdrawal
- possible: good timing, other cause possible
- unlikely: poor timing, other cause more likely
- unassessable: insufficient or contradictory information

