Trial-specific Discussion of Intervention Risks and Mitigations

There is a risk that even though the partial meniscal replacement is performed, the knee functionality will not improve. Strict inclusion and exclusion criteria should limit the number of cases without a benefit (see inclusion and exclusion criteria). The treatment would be the same, participating or not on the trial. Study specific is to fill the questionnaires at the planned visits (IKDC and KOOS, CRF).

Trial-specific Discussion of Procedure Risks and Mitigations

The procedure risks are the risk of any surgery for the operated group. The non-operated group does not have any surgical risk. They have the risk that the knee functionality will deteriorate. Due to the close follow-up, also for these patients, they can minimize this risk by deciding to change into the operated group.

Trial-specific Discussion of Other Risks and Mitigations

There are no other risks. There are no comparators, challenge agents or medical devices.

Overall Benefit: Risk Conclusion

The overall risk is very low, because partial meniscal replacement is an established operative procedure.

There are the normal risks applying to any surgical procedure. For the non-operated group, there are no surgical risks.

The benefit for the surgical group is the possibility of improvement of knee functionality. The benefit for the non-operated group is the close follow up to monitor the properties of the meniscus. This will help to decide to switch to the surgery group. The risks are assessed at least once a year for up to 2 years. After this treatment related risks are not expected. The 5-year visit is scheduled to verify the properties of the meniscus and to evaluate the exploratory outcome of progression of osteoarthritis up to TKA.

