7.1.3 Rechallenge

Because the treatment is finished after the surgery, there is no re-challenge possible for patients in the operated group. Patients from the non-operated group can change to the operated group, but this is than no rechallenge, but the start of the trial as described under 1.2 Trial Scheme.

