11 GENERAL CONSIDERATIONS: RISK MANAGEMENT AND QUALITY ASSURANCE

11.1 Quality Tolerance Limits

Quality tolerance limits are defined in the inclusion/exclusion criteria. The main criteria which may lead to exclusion of the patient from the trial are age (must be over 18 years and under 60 years) and BMI (must be $<30 \text{ kg/m}^2$). The investigator expects a 20% drop in total. If the drop-out will be higher, this could significantly impact the study results. Protocol deviations and violations will not occur, because the surgery is performed after a standardized procedure. The patient does not have any impact on this procedure.

The percentage of withdrawal will be small, because the burden of the trial is very low (filling the 3 questionnaires at the follow-up-visit). The investigator predicts a maximum of 5 % withdrawal, which is included in the 20% mentioned above.

Incomplete data will occur due to lost to follow-up, withdrawal or due to progression of osteoarthritis up to TKA. Progression of osteoarthritis is a very slow process; thus a 2.5% possibility would be defined by the investigator for incomplete data related to progression of osteoarthritis up to TK.

AE and SAE occur at any time and may be not related to the IMP used. SAE not related to the investigational product do not impact study results. SADR/SUSAR's do impact study results. Because human allogeneic cortical bone (in any supply form) was transplanted in different forms several thousand-fold, the manufacturer (DIZG gGmbH, Berlin, Germany) did not receive any information about and SADR or SUSAR up to now.

The IMP is not a pharmacological drug and the administration is not over the trial period. The IMP will be implanted during surgery and remains in the body. It has no systemic effect and it is not a medical device.

Patient follow-up will be the same for patients included in the trial or not, thus the lost to follow-up will be below 10 %, because the follow-up-visits are only a minimal burden.

For ethical reasons, there is no randomization in the trial. The patient decides, if he will be operated, or not. Even if the patient will decide not to be operated in the first round, they have the possibility to change to the surgery group at any time. Thus, there is no pressure on the patient and there is no incorrectly randomized patient.

All this Quality tolerance limits are monitored during the trial via a clinical monitor (CRA).

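### The causality criteria in 12.4 are written for a drug, so a clear graft event with the graft in place can be graded no higher than 'possible'

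*Protocol*

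**What the plan says.** Protocol 12.4 lists six causality categories and then gives short criteria under a WHO label. The three that assert a relation are:

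- "definitely related: good timing, no other cause, withdrawal response plausible, rechallenge"
- "probable: good timing, other cause unlikely, withdrawal"
- "possible: good timing, other cause possible"

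*Unlikely* pairs poor timing with a more likely other cause, and *unassessable* covers insufficient or contradictory information. The sixth category, "Causality ruled out/unrelated", appears in the list but has no criterion. Good and poor timing are not defined.

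On the product, 7.1.3 says "there is no re-challenge possible for patients in the operated group", and 11.1 says "The IMP will be implanted during surgery and remains in the body".

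On duration of risk, 2.2 says "The risks are assessed at least once a year for up to 2 years. After this treatment related risks are not expected". It continues: "The 5-year visit is scheduled to verify the properties of the meniscus and to evaluate the exploratory outcome".

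On use of the grade, 8.4.4 has causality recorded for AEs and SAEs. The safety endpoint in 3.2 is restricted to treatment-related AEs and SAEs, while the variable given in the same section is the number of AEs and SAEs without that restriction.

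**The concern.** Withdrawal and rechallenge are tests for a product that can be stopped and given again. This product is implanted once and left in place. If the two higher grades depend on those tests, the clearest graft-related event ends in the same grade as an event with a plausible competing explanation, and the scale cannot separate them.

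The grade has several uses. It defines the endpoint as named in 3.2. It decides which SAEs go to EudraVigilance as IMP-related (8.4.6), and it bears on what is suspected for SUSAR reporting (8.4.8). SAEs causally related to the implant are listed among the reasons for premature termination (10.5). The judgement is made by one investigator who is also the sponsor, with no committee (10.2), so the written criteria matter more than they would with independent adjudication.

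The 2.2 wording adds a second question: whether the plan treats safety as closed at 2 years although follow-up runs to 5.

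**Working it through.** No figure in the plan has to be reproduced; the check is a comparison of texts.

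**Step 1. Grade a test case.** Take an event in the operated knee that arises from the graft, with good timing and no other cause. Compare it with each 12.4 category, reading the listed elements as all required.

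| Category | Graft in place | Graft removed |
|---|---|---|
| Definitely related | Not met: no withdrawal, and rechallenge excluded by 7.1.3 | Not met: rechallenge still excluded |
| Probable | Not met: no withdrawal, since the graft stays (11.1) | Can be met |
| Possible | Nearest fit, although its wording supposes another possible cause | Nearest fit |
| Unlikely | Not met: timing is good and no other cause is more likely | Not met |
| Unassessable | Not met: information is sufficient | Not met |
| Ruled out/unrelated | No criterion to apply | No criterion to apply |

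Of the 3 grades asserting a relation, 1 can be reached with the graft in place, 2 with it removed, and *definitely related* in neither case. Criteria exist for 6 − 1 = 5 of the 6 categories. A later move from the non-operated to the operated group does not supply a rechallenge either, because 7.1.3 says so expressly.

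**Step 2. Move the same event to years 3 to 5.** Nothing in 12.4 says when timing becomes poor, and 12.4 does not refer to 2.2. Even if timing were called poor, *unlikely* also asks for a more likely other cause, which the test case lacks. So no written rule sends this event to *unlikely*.

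**Step 3. Compare 2.2 with the operative sections.** Section 2.2 describes risk assessment up to 2 years and gives the 5-year visit a meniscus and exploratory purpose only. Section 1.3 schedules complications and reoperation at U6, 8.4.2 collects AEs and SAEs at 5 years and whenever they are reported, and section 9 evaluates complications, AEs, SAEs and SUSARs at each visit including 5 years. The summary text is narrower than the sections that govern conduct.

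**Step 4. Compare the 3.2 endpoint with the analyses.** The endpoint and the population-level summary in 3.2 are limited to treatment-related events. The 3.2 variable is not, and 9.1, 9.3 and 9.5 compare AEs and SAEs between groups with no relatedness filter.

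**Step 5. Trace where a wrong grade would travel.** Independent of the grade: collection of events (8.4.2), the group comparisons (9.1, 9.3, 9.5), SAE reports to the ethics committee and authorities (8.4.6, 8.4.7), and the benefit-risk re-evaluation triggered by AEs or SAEs (7.4, 9.7). Dependent on it: the recorded causality itself, the endpoint as named in 3.2, and the IMP-related route to EudraVigilance. The protocol does not say which grades count as related, and nothing excludes *possible*.

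**The case against.** The strongest reply is that losing the two upper grades changes nothing that is reported. An event graded *possible* can still count as treatment-related, and SUSAR reporting rests on suspicion rather than proof. This largely stands: it limits the effect to grading. It does not rescue the scale, which still gives the clearest case a grade worded for a less clear one.

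A second reply is that the criteria are comma-separated shorthand under a WHO label, and 12.4 does not say that every element is mandatory. That is fair. The result in Step 1 depends on reading the elements together, and the cited scheme is not available to settle it. But someone grading from the protocol has only these words, and no implant-specific substitute is offered.

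Third, a reader might infer from 2.2 that graft events in years 3 to 5 will be systematically under-attributed. The documents do not support that. No rule makes 2 years a cut-off, *unlikely* needs a more likely cause as well as poor timing, and saying that risks are not expected is not saying that they go unassessed. Section 12.1 also names swelling, infection at the operated site and pain in the treated knee, among others, as trial related with no time limit, so several likely presentations of a late graft problem are already covered.

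Finally, the 2.2 and 3.2 points are separate from the criteria in 12.4. That is correct. They are included because they concern the same safety evaluation and can be corrected in the same edit.

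**Conclusion.** The point holds as a drafting defect of minor priority. Section 12.4 states criteria that 7.1.3 and 11.1 make unattainable or attainable only by explantation, so a clear graft event with the graft in place is graded at best *possible*, and one of six categories has no criterion. This is a rule stated in the protocol that fits the product badly, not detail left for a later document.

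The consequence is mainly misgrading. It would be tempting to go further and say that safety data are lost after 2 years, that a stopping decision would be missed, or that a mandatory report would not be made; Step 5 shows none of these. The protocol gives no rate of late graft events, so the number of misgraded events cannot be stated.

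The conclusion assumes that the elements listed for each grade are all required. If *possible* is treated as related, which the protocol neither states nor excludes, the 3.2 endpoint and the EudraVigilance route are unaffected for the test case in Step 1. The inconsistencies in 2.2 and 3.2 hold whichever way 12.4 is read.

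**What to change.** - **12.4:** replace withdrawal and rechallenge with criteria suited to an implant: event in the index knee; graft involvement on the MRI already scheduled, or on arthroscopy if done for clinical reasons; presence or absence of another cause. Give a criterion for all six categories. State that *possible* and above count as related, and that time since surgery alone does not make an event unlikely.
- **2.2:** replace the 2-year wording with a statement that AEs, SAEs, complications and reoperations are collected and assessed for causality through 5 years.
- **3.2:** name all AEs and SAEs as the safety endpoint, with treatment-related ones as a subset, so that it agrees with its own variable and with 9.1, 9.3 and 9.5. Change the matching synopsis row in 1.1 in the same way.

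The cost is text in these sections, with the CRF causality guidance matched to 12.4. No visit, procedure or patient is added. The downside is that somewhat more events will be graded as related.

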13 APPENDIX: DEFINITIONS AND SUPPORTING OPERATIONAL DETAILS

13.1 Contraception and Pregnancy Testing

13.1.1 Definitions Related to Childbearing Potential

Participants of childbearing potential are females which can become pregnant. These patients can take part in the study, but when they decide for the operated group, they must make a pregnancy test before surgery. After surgery they can become pregnant. This does not influence study results.

All patients with non-childbearing potentials are male or female after menopause. They can take part in the study without a pregnancy test.

13.1.2 Contraception

Contraception does not have to be taken. A pregnancy test before surgery is sufficient for childbearing potential patients who wish to be operated.

13.1.3 Pregnancy Testing

Pregnancy testing is only required for patients who will be operated and have childbearing potential.

13.2 Clinical Laboratory Tests

Trial specific laboratory testing is not necessary and not planned. Only the normal laboratory testing will be performed for patients who will be operated.

13.3 Country/Region-Specific Differences

The trial will be conducted only in Germany, there are no country/region specific differences to the above explained rules.

13.4 Prior Protocol Amendments

This protocol has not been amended

14 APPENDIX: GLOSSARY OF TERMS

Abbreviations

| | |
|-----------------|--|
| AE; | Adverse event |
| BfArM | Bundesinstitut für Arzneimittel und Medizinprodukte |
| CMI: | Collagen Meniscus Implant |
| FSA-Kodex: | freiwillige Selbstkontrolle der Arzneimittelindustrie |
| ICRS | International Cartilage Repair Society |
| IKDC: | International Knee Documentation Committee Score |
| IMP: | investigational medicinal product |
| IRB/IEC | Institutional Review Board/Institutional Ethic Committee |
| KOOS: | Knee injury and Osteoarthritis Outcome Score |
| PEI | Paul Ehrlich Institut |
| PROM: | Patient Recorded Outcome Measures |
| SADR: | Serious adverse Drug reaction |
| SAE: | Serious adverse event |
| SUSAR: | Suspected Unexpected Serious Adverse Reaction |
| TKA: | total knee arthroplasty |
| VAS Pain Score: | Visual analogue pain scale |

